## 8.2 Statistical Methods

### 8.2.1 Efficacy Analyses

#### Primary Efficacy Analyses:

The average treatment effect (ATE) for the investigational product will be estimated using a linear regression of the 10-minute post-treatment bacterial count ( $\log_{10}$  scale) on the additive effect of a treatment indicator and the baseline measurement ( $\log_{10}$  scale). The lower bound of the 95% confidence interval for the additive treatment effect must not include the investigational product being more than  $0.5 \log_{10}/\text{cm}^2$  lower than the positive control.

The ATE of the test product compared to the negative control is estimated as the contrast of treatment effect of negative control minus the treatment effect of the test drug in the linear regression. Likewise, the ATE of the active control compared to the test product is estimated as the contrast of treatment effect of test product minus the treatment effect of the active control in the linear regression. Superiority to negative control uses a margin of  $1.2 \log_{10}/\text{cm}^2$ , which would be demonstrated by a lower bound of the 95% confidence interval for the contrast to exceed  $1.2 \log_{10}/\text{cm}^2$ .

The percent of samples for which the 6-hours post treatment recovery is lower than the baseline recovery will be calculated by active product. The Final Monograph requires that these percentages be 100.

#### Secondary Efficacy Analyses:

Summary tables will be produced by treatment for  $\log_{10}/\text{cm}^2$  baseline skin flora,  $\log_{10}/\text{cm}^2$  recovery of skin flora, and  $\log_{10}/\text{cm}^2$  reduction of skin flora relative to Treatment Day baseline  $\log_{10}/\text{cm}^2$  on the inguinal region at 10 minutes and 6 hours following application of the study materials. The tables will include number, mean, standard deviation, minimum and maximum.

### 8.2.2 Safety Analysis

Adverse events and skin irritation scores will be summarized by product.

## 8.3 Data Sets Analyzed

A modified intent-to-treat data set will be used for primary efficacy analysis. All subjects who meet baseline requirements on a bilateral side will be included in the analysis for that bilateral side. However, the primary analyses involve a linear regression at the 10-minute post-treatment

**[name]**

time point and calculation of return to baseline at 6 hours. These analyses cannot be done without both baseline and 10-minute recovery for treatment effect or baseline and 6-hour recovery data for return to baseline percentage calculation. The exclusion of subjects who do not meet baseline requirements and who are missing recovery data at one or both of the post-treatment sampling times makes this data set a modified intent-to-treat data set.

The baseline bacterial count requirements are in the range of 5.00 to 7.50  $\log_{10}/\text{cm}^2$  on the groin. The acceptability of each bilateral baseline will be assessed separately for inclusion in the study.

The full intent-to-treat data set (all randomized subjects) will be used for the safety analysis.

#### **8.4 Criteria for the Termination of the Study**

3M reserves the right to terminate the study at any time for business reasons.

#### **8.5 Procedures for Accounting for Missing, Unused, and Spurious Data**

Details of any other missing data handling will be specified in the statistical analysis plan.

#### **8.6 Deviations to Statistical Plan**

A statistical analysis plan (SAP) will be written and approved prior to study initiation. Any deviation from the original SAP will be described and justified in the final report.

### **9. MONITORING**

3M, as sponsor of this study, is responsible for ensuring the proper conduct of the study with regard to protocol adherence and validity of the data recorded. 3M has therefore assigned a study monitor to this study. The progress of the study will be monitored by:

- Periodic on-site review
- Ongoing review of electronic documentation via Clindex
- Telephone and e-mail communications
- Review of source documents

The Investigator or designee will give the 3M study monitor direct access to source documents that support data on the eCRFs and make available such records to authorized 3M, quality assurance, IRB, and regulatory personnel for inspection and/or copying.

Note: The Federal Privacy rule (HIPAA) specifically permits the use and disclosure of protected health information “to a person subject to the jurisdiction of the Food and Drug Administration (FDA) with respect to an FDA-related product or activity for which that person has responsibility, for the purpose of activities related to the quality, safety, or effectiveness of such FDA-regulated product or activity.”

[name]

## 10. QUALITY CONTROL AND QUALITY ASSURANCE

3M is responsible for implementing and maintaining quality assurance and quality control systems through written standard operating procedures (SOPs) to ensure that this study is conducted and data are generated, documented and reported in compliance with the protocol, GCP and regulations cited in Section 1.4 of this protocol. Study monitoring is carried out to accomplish this.

## 11. ETHICS

This study will be conducted in accordance with the principles that have their origin in the Declaration of Helsinki, 21 CFR 50 (Informed Consent) and 56 (IRBs).

The study will start only after approval of the protocol and consent form by the IRB. The approval letter or notice must contain the IRB name, meeting date, and sufficient information to identify the protocol and informed consent by name and number that were reviewed. 3M, prior to study initiation, must receive a copy of the IRB approval letter.

## 12. DATA HANDLING AND RECORD KEEPING

### 12.1 Study Personnel

Prior to study initiation, the Investigator must provide 3M with a signed Form FDA 1572. This form identifies all sub-investigators who will be assisting the Investigator in the conduct of the study. The Investigator will provide a log of signatures/initials prior to study initiation.

### 12.2 Pre-Study Documentation Requirements

Prior to study initiation, the Investigator must provide 3M with the following documents:

- Signed protocol including any amendments in place prior to study initiation
- Curriculum vitae for the Investigator and any sub-investigators
- IRB approved consent/authorization form
- IRB study approval letter
- IRB name, location and chairperson
- IRB membership list
- Signed Form FDA 1572
- Financial Disclosure documents per 21 CFR 54
- Signed research agreement

### 12.3 Completion and Return of Case Report Forms

Electronic data capture (eDC) will be used for this study. The site will be trained on the eDC software prior to study enrollment. The site will be provided with a manual, including instructions on how to complete the eCRFs and how to make eCRF corrections within the eDC software. Microbiological count data will be recorded onto DCSs prior to entry into the eDC

3M Confidential

Document Name: CLIN-PROT-ICH-US-05-658998

Clinical and Non-Clinical: CLIN-INDEX-3M-SPON-US-05-014624

**[name]**

system. The Investigator must review and electronically sign eCRFs in a timely fashion following the 3M study monitor's review.

#### **12.4 Final Report**

The Investigator will submit an Investigator Final Report to 3M within one month of the completion of statistical analysis or termination of the study. 3M will be provided a draft Investigator Final Report for review. The Investigator will make reasonable changes deemed necessary by 3M and finalize. The Investigator will submit the Investigator Final Report to 3M and the IRB.

3M will prepare and submit a Sponsor Final Report to the FDA. The study medical monitor will sign the Sponsor Final Report.

#### **12.5 Records, Reports and Retention Requirements**

Study records must be kept until 3M provides notification that the documents can be destroyed. This may extend beyond the 2 years required by law. In order to comply with regulatory requirements, the Investigator must arrange for the retention of all study records for 2 years following the date a marketing application is approved for the drug and indication investigated, or if no application is filed, until 2 years after completion/termination of the study.

Records to be retained by the Investigator include, but are not restricted to:

- Signed study protocol, amendments, deviations
- IRB approval of protocol, consent form, authorization form, waiver of consent and/or authorization and amendments to any of these documents
- Applications to the IRB
- Signed consent/authorization forms
- DCSs
- eCRFs
- Records of receipt, use or disposition of the investigational drug
- Correspondence relating to the study
- Investigator Brochure
- Financial disclosure documents
- Sponsor Final Report
- Investigator Final Report

## 14. APPENDICES

### 14.1 Study Flow Diagrams

#### Screening

## Treatment

[name]

## 14.2 Study Product Application Instructions

Study personnel must use sterile gloves to apply the solutions.

### Treatment Code: SP (SoluPrep)

1. Aseptically remove investigational product from sterile packaging and maintain sample in a sterile environment prior to sample application.
2. With the sponge in a downward position, snap the lever on the applicator allowing the fluid to flow into the sponge. Wait until the sponge fills completely.
3. Apply the product with repeated back-and-forth strokes for 2 minutes on the groin.
4. Do not allow solution to pool. Use sponge applicator to absorb excess solution and continue to apply.
5. Allow the test area to dry for 3 minutes.
6. Contact time begins after step 5.
7. Residual product should be removed from test areas after the final sample collection is complete using alcohol wipes or soap and water.
8. Record the subject number on the package label and retain for inventory purposes. Discard used applicators.

### Treatment Code: SPFF (SoluPrep FF)

1. Aseptically remove investigational product from sterile packaging and maintain sample in a sterile environment prior to sample application.
2. With the sponge in a downward position, snap the lever on the applicator allowing the fluid to flow into the sponge. Wait until the sponge fills completely.
3. Apply the product with repeated back-and-forth strokes for 2 minutes on the groin.
4. Do not allow solution to pool. Use sponge applicator to absorb excess solution and continue to apply.
5. Allow the test area to dry for 3 minutes.
6. Contact time begins after step 5.
7. Residual product should be removed from test areas after the final sample collection is complete using alcohol wipes.
8. Record the subject number on the package label and retain for inventory purposes. Discard used applicators.

**Treatment Code: S (Sterile 0.9% saline – 20 mL bottle, with sponge applicator)**

1. Remove petri plate from sleeve. Place lid sterile side up on bench.
2. Pour 20 mL sterile saline into lid.
3. Aseptically remove applicator from sterile packaging.
4. Holding applicator handle place one side of sponge into saline, allowing fluid to flow into sponge. Gently press sponge against lid until saturated. Flip sponge and repeat, ensuring both sides of sponge are completely saturated with fluid.
5. Apply the product with repeated back-and-forth strokes for 2 minutes on the groin, flipping applicator as needed to ensure the test area remains wet during product application.
6. Allow the test area to dry for 3 minutes.
7. Contact time begins after step 6.
8. Record the subject number on the package label and retain for inventory purposes. Discard used applicators.

#### 14.3 Confirmation of Release & Receipt of Clinical Supplies

##### **CONFIRMATION OF RELEASE & RECEIPT OF CLINICAL SUPPLIES**

**Investigator:** M. [name]  
**Study No:** EM-05-014264, MBT #109-296  
**Test Site:** Microbac

Qty	Item Name	ID/Lot Number	Exp. Date

Supplies Released to Site by: \_\_\_\_\_  
Monitor's Signature

Supplies Sent to Site (Date): \_\_\_\_\_

Supplies Checked and Verified by: \_\_\_\_\_  
Signature \_\_\_\_\_ Date \_\_\_\_\_

\_\_\_\_\_  
Print Name, Title

Once the supplies have been verified and this form is signed / dated, please scan and email a copy to [name] at [contact].

**[name]**

## 14.4 Study Product Disposition Form

As an investigator, you are required to record disposition of clinical study products. This form is supplied for your convenience in fulfilling this obligation. Use one form for each study product.

Study Number: EM-05-014264, MBT #109-296	Protocol Title: Assessment of the antimicrobial efficacy of 3M™ SoluPrep™ Preoperative Skin Preparation against resident human skin flora on the inguinal region
Investigator: M. [name]	Investigator Site: Microbac

Investigational Material ID:	Date Received:	Quantity Received:	Lot Number/Serial Number:	Date Returned to Sponsor:

[name]

#### 14.7 Test Site Diagram

Follow the randomization schedule for each subject for the exact placement of test materials.

3M Confidential

Document Name: CLIN-PROT-ICH-US-05-658998  
Clinical and Non-Clinical: CLIN-INDEX-3M-SPON-US-05-014624

[name]

#### 14.8 Skin Irritation Rating Scale

Skin Irritation Rating Scale (Modified Draize)		
Condition	Rating	Description
Erythema	0	No reaction
	1	Mild and/or transient redness limited to sensitive area
	2	Moderate redness persisting over much of the product-exposed area
	3 a	Severe redness extending over most or all of the product-exposed area
Edema	0	No reaction
	1	Mild and/or transient swelling limited to sensitive area
	2	Moderate swelling persisting over much of the product-exposed area
	3 a	Severe swelling extending over most or all of the product-exposed area
Rash	0	No reaction
	1	Mild and/or transient rash limited to sensitive area
	2	Moderate rash persisting over much of the product-exposed area
	3 a	Severe rash extending over most or all of the product-exposed area
Dryness	0	No reaction
	1	Mild and/or transient dryness, limited to sensitive area
	2	Moderate dryness persisting over much of the product-exposed area
	3 a	Severe dryness extending over most of the product-exposed area

a = A rating of 3 on the skin irritation scale will be recorded as an Adverse Event.

[name]

## 14.9 Protocol for Neutralization Validation

### 14.9.1 Background

In order to accurately assess the efficacy of an antimicrobial product, it is necessary to completely inactivate the antimicrobial agent at the time point being evaluated. Inadequate neutralization will allow killing or inhibition of the microorganisms to continue beyond the specified contact time, resulting in an overestimation of antimicrobial activity.

Standard sampling solution (SSS) is a buffered detergent solution that is commonly used in studies where microbial sampling of skin is conducted. Neutralizers have been added to inactivate the antimicrobial, CHG, present in the investigational and marketed active study products. Modified Sampling Solution (MSS) is a 1 to 6 ratio of Triacetin to SSS. Triacetin is a fully saturated triglyceride, commonly used as an emollient, and is required to dissolve the film formed by SoluPrep FF. The MSS is used to neutralize SoluPrep and SoluPrep FF. The effectiveness and nontoxicity of these neutralizer systems must be assessed to demonstrate that there is no effect on the growth of microorganisms and that the antimicrobial ingredient is inactivated.

The density of normal human skin flora generally ranges from  $10^2$  to  $10^8$  CFU/cm^2 depending on the body site. However, since significant neutralizer or toxic effects are more easily detected at a lower cell density, the efficacy and toxicity of these neutralizers will be assessed against a lower bacterial concentration.

This is an *in vivo* test where the active study products are applied to the skin using the same application instructions used for the inguinal region during the study (Appendix 14.2). Scrub cup samples are collected and inoculated with low levels of methicillin-resistant *Staphylococcus epidermidis* (MRSE) or methicillin-sensitive *Staphylococcus epidermidis* (MSSE). Two contact times after inoculation will be evaluated: immediately (<1 minute) and 40 minutes (to test for residual antimicrobial activity between sample collection and the time of plating).

### 14.9.2 Objective

The objective of this assay is to determine the ability of the sampling solutions to completely neutralize the active ingredients contained in SoluPrep and SoluPrep FF when applied to the abdomen of test subjects without exhibiting toxicity to the test organisms.

### 14.9.3 Subject Entry Criteria

[figure not shown]
Six subjects will participate in this study. Subjects must meet the inclusion and exclusion criteria in Sections 4.1 and 4.2 of the protocol to which this neutralizer validation is attached, except for the baseline bacterial count, the 72-hour exclusion from showering/bathing and the length of the washout period. The neutralization subjects do not require a minimum baseline count and they only need to avoid topical and systemic antimicrobials for 7 days (not 14 days) prior to

**[name]**

Treatment Day. Subjects will be asked to provide information on demographics and inclusion/exclusion criteria and sign the Informed Consent and Authorization Forms before beginning the 7-day washout period. When subjects return to begin their participation in the study they will again be asked to provide information relative to inclusion/exclusion criteria. If they meet all inclusion/exclusion criteria, they may be enrolled. These subjects will be identified by the letter "N" for neutralization and a subject number starting with 001.

Each subject will receive both active study products (SoluPrep and SoluPrep FF), which will be applied to 2 separate test areas on the abdomen. One area will be located on each side of the body as indicated in the diagram below.

**Neutralization Test Area Diagram**

#### **14.9.4 Test Organism**

The test organisms for this study are methicillin-resistant *Staphylococcus epidermidis*, ATCC 51625, and methicillin-sensitive *Staphylococcus epidermidis*, ATCC 12228.

#### **14.9.5 Study Products**

- SoluPrep, 10.5-mL, tinted
- SoluPrep FF, 10.5-mL, tinted

[name]

#### 14.9.6 Materials, Supplies and Equipment

- Product kits (toiletry items to be used by subjects during study)
- Subject Informed Consent / Authorization forms, IRB-approved
- Standard Sampling Solution (SSS), 75mM phosphate buffer (0.04% monobasic potassium phosphate, and 1.01% dibasic sodium phosphate) containing 0.1% Triton® X-100, 0.3% lecithin, 3.0% polyoxyethylene sorbitan monooleate (Tween® 80), and 1.0% Tamol™ SN; pH  $7.9 \pm 0.1$ , sterile
- Triacetin (provided by sponsor)
- Butterfield's sterile phosphate buffered water (PBW), 312  $\mu$ M KH2PO4, pH  $7.2 \pm 0.1$
- 70% Isopropyl alcohol (w/w) swabs/wipes
- High-purity deionized water, sterile
- Trypticase soy broth (TSB)
- Trypticase soy agar (TSA)
- Trypticase soy agar containing 0.5% Tween 80 and 0.07% lecithin (TSA+N)
- Methicillin-resistant *Staphylococcus epidermidis* (MRSE), ATCC 51625
- Methicillin-sensitive *Staphylococcus epidermidis* (MSSE), ATCC 12228
- Alcohol wipes
- Transfer pipettes, polyethylene, sterile
- Serological pipettes, 1 mL, 2 mL, and 10 mL, sterile
- Pipettor, calibrated to accurately deliver volumes of 0.5 mL, 2.5 mL and 3.0 mL, and sterile tips
- Pipetting, calibrated to accurately deliver 20-200  $\mu$ L, and sterile tips
- Tubes with sealable caps, polypropylene or glass, sterile
- Petri dishes, 100 mm, sterile
- Gloves, sterile
- Marking templates, 1.5" x 5", sterile (for marking test sites)
- Non-toxic marking pen (Sharpie or equivalent), sterile (Note: Do not use markers containing crystal violet)
- Scrub cups (2.20 cm I.D., 3.80 cm^2), sterile
- Teflon or rubber policemen, sterile
- Timers or stopwatches
- Pipet Aid or similar apparatus
- Vortex mixer
- Water bath ( $45 \pm 2$ °C)
- Incubator ( $30 \pm 2$ °C)
- Surgical clippers with blades

#### 14.9.7 Study Procedures

##### 14.9.7.1 Preparation of Inoculum

Prepare an overnight ( $24 \pm 4$  hours) broth culture of each of the test organisms at  $35 \pm 2$ °C in TSB, to contain approximately  $10^8 - 10^9$  CFU/mL.

**[name]**

Dilute the overnight cultures with PBW to achieve an appropriate concentration (approximately  $10^4$  CFU/mL) for inoculation of the test samples. The density of the test inocula must be verified by direct plating at the beginning and end of the study.

#### **14.9.7.2 Preparation of Test Areas and Post-Prep Sampling**

Neutralization samples will be evaluated on the abdomen. The test areas on each subject's abdomen will be assigned according to a computer-generated randomization schedule to receive either the investigational product on the left and the active control on the right or the investigational product on the right and the active control on the left. The subject number, location of the product application, location of the sites sampled within the test area, and the time of sample collection will be documented. Each subject will be treated with both study products, one in each test area.

Abdominal test areas will be marked using a sterile 1.5" x 5" template. One 1.5" x 5" area will be delineated on each side of the body with each area containing two 1" x 1" sampling sites (one sampling site will be used for each test organism) to yield 4 sampling sites for each subject (see neutralization test area diagram in Section 14.9.3 of the neutralization validation). One tube from each test area will be inoculated with MRSE and the other will be inoculated with MSSE.

After the test areas are marked, each area will be prepped with three 70% isopropyl alcohol swabs for a total of 1 minute and allowed to dry for 3 minutes.

Each test area will be treated with 1 of the 2 study products, according to the instructions for the inguinal region provided in Appendix 14.2 of the protocol to which this neutralizer validation is attached.

Samples will be collected, using the scrub cup technique, at 10 minutes ( $\pm$  30 sec.) post-prep. Post-prep timing begins upon completion of study product application, including the 3-minute drying time. For the two sites within each 1.5" x 5" area; the samples may be collected simultaneously by two technicians. The sampling technique is described in Section 5.3.4.1 of the protocol to which this neutralizer validation is attached.

Residual product should be removed from test areas after sample collection is complete using alcohol wipes.

Each pooled sample (~6 mL) will be capped tightly and pulsed 3 times on a vortex mixer. Sample tubes will be sonicated 2 minutes followed by vortex mixing for 30 seconds. Five mL will be transferred to a clean tube and immediately inoculated with 100  $\mu$ L of the appropriate diluted inoculum (Section 14.9.7.1 of the neutralization validation). This will yield an organism concentration of ~20 – 200 CFU/mL.

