##### Modified Sampling Solution (MSS):

A sterile scrub cup will be placed and held firmly on each site. **Scrub 1:** 1.0 mL of Triacetin and 2.0 mL of SSS will be aseptically pipetted into the scrub cup. The skin will be scrubbed in a circular motion with moderate pressure for 1 minute using a sterile policeman. Using a sterile transfer pipette, the scrub solution will be transferred to a sterile collection tube. **Scrub 2:** An additional 3.0 mL of fresh SSS will be pipetted into the scrub cup and the scrub procedure will be repeated. This solution will be pooled with the solution from Scrub 1 for a total sample volume of approximately 6 mL per site.

Following collection, each sample tube will be capped tightly and pulsed 3 times on a vortex mixer followed by a 2-minute sonication and 30-second vortex. A 1.0 mL aliquot of each sample will be diluted into sterile tubes containing 9.0 mL PBW. Serial 10-fold dilutions will be performed in PBW. One-milliliter (1.0-mL) aliquots of selected dilutions will be pour-plated in triplicate using TSA+N. **Samples must be plated within 30 minutes of collection. Plated samples must be well swirled.** Each plate should be labeled with the subject treatment number, anatomical region sampled (groin), test site sampled (right or left and time point), and dilution plated. After 72 ( $\pm$  4) hours of aerobic incubation at  $30 \pm 2^\circ\text{C}$ , colonies will be counted and viable cells in the original sample will be calculated using standard methods. Following incubation, plates may be refrigerated for up to 48 hours prior to counting.

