**[name]**

Immediately (<1 minute) and at 40 minutes ( $\pm$  2 minutes) post-inoculation, 1.0-mL aliquots of the inoculated samples will be pour-plated in triplicate using TSA+N. Plates will be incubated inverted at  $35 \pm 2^\circ\text{C}$  for  $48 \pm 4$  hours.

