##### Numbers Control (NC):

Add 100  $\mu\text{L}$  of the appropriate diluted inoculum to a tube containing 5 mL PBW to yield final inoculum concentrations of  $\sim$ 20-200 CFU/mL. Sonicate 2 minutes followed by vortex mixing for 30 seconds. Pour-plate triplicate 1.0 mL aliquots immediately (<1 minute) and 40 minutes (+ 2 minutes) post-inoculation in the same manner as 14.9.7.2, except using TSA without neutralizers.

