##### Neutralizer Effectiveness:

If the mean  $\log_{10}$  CFU/mL of the sample is not more than 0.3  $\log_{10}$  less than the mean  $\log_{10}$  CFU/mL of the NC, the neutralization will be considered effective.

- Mean  $\log_{10}$  CFU/mL from NC – Mean  $\log_{10}$  CFU/mL from sample (use corresponding time points)

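### The neutralizer validation inoculates product samples and the toxicity control after sonication but the numbers control before it, so both 0.3 log10 pass rules compare unlike-handled tubes and the first minutes after collection go unchallenged

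*Combined protocol and SAP*

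**What the plan says.** Protocol Appendix 14.9.1 gives the aim of the two contact times: "to test for residual antimicrobial activity between sample collection and the time of plating". Both times are counted from inoculation.

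For product samples, 14.9.7.2 puts the processing first and the organism after it: a 2-minute sonication "followed by vortex mixing for 30 seconds. Five mL will be transferred to a clean tube and immediately inoculated" with 100 µL of diluted inoculum. Plating is set as "Immediately (<1 minute) and at 40 minutes" (± 2) post-inoculation.

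In 14.9.7.3 the TC (Triacetin plus SSS, no product) is mixed, sonicated and vortexed; 5 mL is then transferred and inoculated. The NC reverses this. The inoculum goes into 5 mL PBW, and then: "Sonicate 2 minutes followed by vortex mixing for 30 seconds". The NC is also to be plated within 1 minute of inoculation.

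Under 14.9.9, if the sample mean is no more than 0.3 log10 below the NC mean at the matching time, "the neutralization will be considered effective". The toxicity rule has the same form, with the TC in place of the sample.

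In the trial itself (5.3.4.1) the skin flora are in the fluid from Scrub 1 onward. After pooling, "each sample tube will be capped tightly and pulsed 3 times on a vortex mixer followed by a 2-minute sonication and 30-second vortex". Plating must follow within 30 minutes of collection.

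**The concern.** A pass rule based on a difference from a control is clean only if the two tubes differ in nothing but the factor being judged. Here the NC organisms go through 2 minutes of sonication and 30 seconds of vortexing, while the sample and TC organisms do not. Sonication could lower counts by damaging cells or raise them by breaking up clusters. Either would shift both criteria without any change in neutralization or toxicity. The controls are also said to show that the organisms are unharmed by the sampling procedures, yet no validation tube sonicates organisms in the sampling solution that the trial uses.

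The order also leaves part of the stated interval untested. In the trial, flora and antiseptic residue are together through scrubbing and processing. In the validation, the neutralizer has been mixed with the residue for minutes before any organism arrives. Killing confined to those minutes could occur in trial tubes and would not be seen here. Appendix 14.9.1 itself notes that inadequate neutralization overstates activity.

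**Working it through.** **1. The plan's own figure.** The inoculum is about 10^4 CFU/mL, with 0.1 mL added to 5 mL (14.9.7.1 to 14.9.7.3).
- 10^4 × 0.1 / 5.1 = 196 CFU/mL.
- 10^3 × 0.1 / 5.1 = 19.6 CFU/mL.

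This reproduces the stated range of about 20 to 200 CFU/mL; the lower end needs an inoculum of 10^3. All three arms use 100 µL into 5 mL, so their starting densities match.

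**2. Order of steps.**

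| Arm | Before inoculation | After inoculation, before first plating |
|---|---|---|
| Product sample | pulse, sonicate 2 min, vortex 30 s, transfer 5 mL | nothing |
| TC | pulse, sonicate 2 min, vortex 30 s, transfer 5 mL | nothing |
| NC | nothing | sonicate 2 min, vortex 30 s |

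**3. NC timing.** 2 + 0.5 = 2.5 minutes lie between inoculation and the earliest possible plating. The limit is under 1 minute, so the two instructions cannot both be followed.

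**4. Effect on the pass rules.** Let s be the log10 loss that sonication and vortexing cause in the NC. The true loss tolerated in the sample or the TC is then 0.3 + s. The documents give no value for s; ±0.1 is an assumption.
- s = 0: 0.3 log10, and 1 − 10^−0.3 = 50% loss passes.
- s = +0.1: 0.4 log10, and 1 − 10^−0.4 = 60% loss passes.
- s = −0.1: 0.2 log10, and 1 − 10^−0.2 = 37% loss passes.

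**5. Unchallenged time.** After collection it is at least 2 + 0.5 = 2.5 minutes. Counting the two 1-minute scrubs, it is at least 4.5 minutes. Pulsing and transfer times are not given and would add to both. Neither control covers this window, because neither contains antiseptic.

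**6. What the 40-minute test bounds.** If residual killing ran at a constant rate, a sample just passing 0.3 log10 at 40 minutes would lose:
- over 2.5 minutes: 0.3 × 2.5 / 40 = 0.019 log10;
- over 4.5 minutes: 0.3 × 4.5 / 40 = 0.034 log10.

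With s = +0.1 the first figure becomes 0.4 × 2.5 / 40 = 0.025. If killing is faster at the start and then fades, the test sets no bound on the early loss.

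**7. Direction.** Hidden killing lowers recovery on the actives but not on saline, so it favours superiority and the 6-hour result. Planning headroom for superiority is 2.26 − 1.2 = 1.06 log10 (protocol 8.1). Equal loss in both actives largely cancels in the non-inferiority contrast. Loss only in SoluPrep FF, the active control, makes non-inferiority harder to show; loss only in SoluPrep makes it easier.

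**The case against.** The strongest reply is that persistent residual activity is well tested: 40 minutes of contact against a 30-minute plating limit. That stands, and it is why the gap is small under constant-rate killing. It does not address activity that fades before the organism is added.

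A second reply is that the TC is handled like the sample, so a sonication effect would show up in NC minus TC. This stands only in part. There the effect is combined with toxicity, and the rule is one-sided. If sonication lowers the NC, both criteria become easier to pass and nothing is flagged. TC minus sample would be free of the mismatch, but no criterion uses it.

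A third reply is that the order is openly stated and the method is based on an ASTM standard. The standard is not available here, so no departure from it is claimed. The inconsistencies lie within the appendix.

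A reader might go further and infer a material hidden kill. For example, 2.5 log10 over 15 minutes (2 application, 3 drying, 10 waiting) is 0.17 log10/min; with 10% to 50% of that persisting for 2.5 minutes, 0.04 to 0.21 log10 would be lost. The documents do not support this. That rate describes undiluted product on skin, not residue in neutralizing fluid, and the 15 minutes are this trial's timings applied to another study's result. Carried on for 40 minutes, the same rates would give 0.67 to 3.3 log10 and fail the 0.3 rule. The figure therefore needs killing that stops just as the organism is added.

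**Conclusion.** The mismatch is real and needs no assumption about kill rates. Both 0.3 log10 rules compare organisms sonicated after inoculation with organisms that were not, and the NC first plating time cannot be achieved as written. The size of the resulting shift is unknown; the 0.2 to 0.4 range rests on the assumed ±0.1 log10.

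The untested window is also real, at least 2.5 minutes after collection, but its importance is conditional. It is about 0.02 log10 if killing is constant, and it cannot be sized if killing is front-loaded, because the documents give no neutralization-rate data. They do not show that neutralization fails or that the trial's contrasts are biased. The case for changing the procedure is that the correction is cheap and makes the acceptance rule mean what it says.

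**What to change.** Use one order in all three arms (sample, NC, TC):
1. Transfer 5 mL immediately after pooling or mixing.
2. Inoculate with 100 µL.
3. Pulse, sonicate for 2 minutes and vortex for 30 seconds.
4. Plate within 1 minute of the end of vortexing, and at 40 minutes post-inoculation.

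Reword the first contact time in 14.9.1, 14.9.7.2 and 14.9.7.3 to match, and state that the two 1-minute scrubs remain untested.

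The 5 mL transfer should come before inoculation. Adding 100 µL to the pool of about 6 mL instead would lower its density relative to the 5 mL controls by log10(6.1 / 5.1) = 0.08 log10, about a quarter of the tolerance. The TC must move with the sample, or it will stay out of step with the NC.

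Cost: the first plating falls about 3 minutes after inoculation (2.5 minutes of processing plus up to 1) instead of under 1 minute, and the 5 mL is drawn before the pool has been sonicated. No subjects, samples or equipment are added. Protocol 5.3.4.3 places this validation before Treatment Day, so the change belongs there.
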